3.5 Inclusion and exclusion criteria

3.5.1 Inclusion criteria:

- Healthy newborn infants with a birth weight equal or above 2.0 kg, will be included in the study between 0-3 days of life.
- Newborn infants have to come from families who are long-term or permanent residents in the defined catchment area for this trial (30 km radius from HLH) in Tanzania.
- Parents are able and willing to complete study visit (including required study procedures) schedules over the six months proposed follow-up, which also includes hospitalizations required for compliance of this study protocol.
- Children less than 6 months of age admitted to hospital with suspected infection, not included in the RCT, will be included in a sub-study. A separate inclusion form is prepared for these children.

3.5.2 Exclusion criteria:

- Multiple Pregnancy
- Birth weight below 2 kg
- Other health problems/illness, obvious congenital malformations.
- Parents not consenting

3.6 Study period

The study period is expected to last for 18 months, which will include recruitment period of one year and a six-month follow-up of all participants.

3.7 Investigational product (IP)

3.7.1 Description and formulation

The IP is a commercially available multi-strain probiotic product (LaBiNIC probiotic drops®, Biofloratech Ltd, Surrey, UK). The product is widely used in the UK (National Health Service) and other countries in Europe. The product also recently received the Pharmacy Grade Certificate A-Grade by the South African Pharmacy Council, valid until 31st of December 2021 (attached copy).

The product is 100% dairy-, gluten-, egg-, soya- and allergen-free. It contains no animal products, no preservatives, no colourings or sweeteners. It is manufactured to GMP and GPP WHO Standards. All batches are microbiologically tested for safety and composition.

3.7.2 Dose preparation and administration

Five drops (0.2 ml) contain 1.8×10^9 CFU *Lactobacillus acidophilus*, *Bifidobacterium infantis* and *Bifidobacterium bifidum* (equal amount of all three strains) will be given by mouth once daily for 4 weeks to “bottle empty”. Bottle contains 5-5.5 ml.

3.7.3. Storage and stability (shelf-life)

Labinic probiotic drops can be stored at room temperature, provided this does not exceed 25 °C for prolonged periods (a few hours at 30 °C causes no degradation). No refrigeration is needed for storage.

3.7.4 Packaging and labelling

Biofloratech Ltd will pack probiotic and placebo in identical packages, and number the packages according to the randomization list.

3.7.5 Accountability

The investigators will ensure that all investigational products (probiotic and placebo) are inventoried and stored as indicated by the manufacturer. Accurate records will be kept regarding the date manufactured, date received, lot number, expiry date and amount received.

3.8 Study procedures

3.8.1 Recruitment of pregnant women and enrolment of study participants

Pregnant women in their last trimester, visited at home or attending their last visit before delivery at HLH, will be informed about the study and asked for consent to let their future child participate in the study. A study research assistant will inform the woman about all aspects of the study, including the importance of performing such a study, and all procedures which will take place during the study period. A thorough explanation will also be given on how the IP/placebo will be administered orally once daily with 5 drops until bottle empty (four weeks). Finally, the importance of completing the dosage of the IP/placebo for the four week-intervention period will also be explained to the woman. Information will be given orally and by information included in a written informed consent form (ICF). If the woman, after this information, agrees for her child to participate in the ProRIDE-Trial, she will be asked to give written consent to screen and enroll the newborn baby in the study. The woman will receive a special information card developed for the ProRIDE-Trial, after delivery and inclusion. During and after delivery, the attending doctor/midwives will identify mothers who have consented to participation and inform the research assistant, who will help coordinate the study. After delivery the new-born baby will be screened for eligibility into the study, and if the baby fulfills the inclusion criteria of the study, the baby will be enrolled and allocated to the randomized product (active probiotics or placebo), which will be initiated on day 0-1 for hospital deliveries or day 0-3 for home deliveries. The mother will be explained and demonstrated how to administer the study product.

3.8.2. Filling of the electronic CRF using RED cap

Mothers who have given consent will be registered by name and address in the consent form. For enrolled babies, four different electronic case report forms (CRF) will be used for the study, three for the study visits and one for adverse events/unscheduled visits due to hospitalization/outpatient's attendance for participants who fall sick during the study period.

ProRIDE Trial in Tanzania

Infant deaths, hospitalizations and sepsis episodes will also be recorded (Appendix 1-6).

Tablet computers with RED cap® software will be provided to research assistants and investigators. Passwords will be created for each research assistant and investigator to get access to the study file in RED cap. Research assistants will have access only to fill in the respective CRF of the study participants they recruit at each visit and they will have no access to change any information entered in RED cap. Only study investigators will have access to change information filled in the RED cap when need arise. Infant's deaths, hospitalisations and sepsis episodes will also be recorded.

3.8.3 Randomization and blinding

Before the start of the study, an independent researcher/statistician will generate a randomization list with the study identification number of patients, from 1 to 2000, and allocated investigational product or placebo. This randomization list will be sent to Biofloratech Ltd, Surrey, UK for labelling of the investigational product and placebo, which will be produced and labelled in identical bottles, numbered from 1 to 2000. Upon screening, the newborn infants will consecutively be allocated (randomized) to the next study identification number and given the corresponding investigational product/placebo. The main bias reducing technique in this RCT is randomization and blinding. A local pharmacist, who is not part of the study will be provided with the randomization list. Both study participants and investigators and care providers will be blinded for assignment of the intervention.

3.8.4 Unmasking in emergency situations

A pharmacist not involved in the study will have access to assignment list. Therefore, the study PI may request unblinding for treatment assignment if needed for medical care of a patient in an emergency situation. However, this is a very unlikely situation given the well-known safety of probiotics in infants, and the lack of known interaction with other important drugs used for any other required therapy.

ProRIDE Trial in Tanzania

3.8.5 Visit schedule and follow-up activities

The follow-up schedule is summarized in Table 1 below. After study randomization, participants will receive follow-up for six months. At enrollment the baby will be weighed and clinical data on mother and child will be entered in the CRF. The first visit after enrolment will be around 7 days after birth, the second at six weeks after initiation of intervention product, and the last visit at six months. During all study visits, the baby's length, weight measurements, and clinical information will be recorded. Fecal samples and fecal swabs will also be taken according to the developed SOP.

Table 1. Follow-up schedule visit for ProRIDE-trial

| Time | Event | Activity |
|----------------------------------------------------------------------|-----------------------------|-------------------------------------------------------------------------------------------------------------------------------------------------------|
| Day 0-3 after birth of the newborn | Enrolment and randomization | - Filling of CRF-1 - Giving the IP/placebo to the mother/caretaker of the baby |
| Day 7 after initiation of investigational product | Visit 1 | - Observe for the compliance - Discuss issues with care takers |
| Six weeks after initiation of investigational product | Visit 2 | -Observe if the bottle with IP/placebo is empty and return the bottle -First fecal and fecal swab sample will be taken -Filling of CRF-2 |
| Six months (25-27 weeks) after initiation of investigational product | Visit 3 | -Second fecal and fecal swab will be taken - Filling of CRF-3 |

3.9 Specimen collection and storage

Standard Operating Procedures (SOP) which have been developed for the study will be used for specimen collection and processing. One fecal sample and one fecal swab sample will be collected at six weeks and six months visits, respectively. The fecal sample will be obtained

ProRIDE Trial in Tanzania

using a commercially available sampling kit (OMNIgen GUT kit, DNA Genotek, Ottawa, Canada) allowing storage of samples at ambient temperatures for up to 7-14 days before DNA extraction. These samples will be transported to HLH latest within 3 days after sampling and at HLH stored in -80 °C freezers. The fecal swab samples will be taken using eSwab (Copan Diagnostics, CA, USA) and frozen at -80 °C freezers until analysis.

During unscheduled visits, when participants or other children below one year of age are hospitalized because of fever, [name] who is the study physician will ensure blood specimens are collected using aseptic technique. The patient's skin and the septum covering the blood culture vial will be disinfected with 70% alcohol (or 1-2% iodine tincture). Plastic gloves, sterile needles and syringes will be used. From the patient, one blood specimen will be collected from the same venipuncture. A total of 4-5 ml of blood will be drawn from the patient for blood culture to investigate for blood stream infections, C-reactive protein (CRP), and also malaria rapid test if clinically relevant. Furthermore, an additional fecal swab sample will be obtained from hospitalized children to investigate correlation between gut carriage of ESBL-E and ESBL-E as a cause for BSI. Caretakers of children <6 months, who are not included in the clinical trial, will be informed about the sepsis sub-study and asked to participate and sign a separate consent form. All children <6 months of age will receive the same diagnostics and treatment whether they are enrolled in the clinical trial, the sepsis sub-study or none of the studies.

3.10 Data collection and handling during the study period

Clinical information as outlined in the CRFs will be recorded for each participant and will be kept confidential. The information will be recorded on electronic CRFs using the RED cap software; a software that globally is widely used for clinical trial purpose. Only informed

ProRIDE Trial in Tanzania

consents will be stored separately. Quality assessment of the data will be done by the internal clinical staffs and consent forms and eCRFs will be checked by external monitors.

3.11 Microbiological methods

3.11.1 Laboratory tests to be performed at Haydom Lutheran Hospital

Blood specimens will be collected during unscheduled visits (hospitalization) of study participants and all children below 6 months of age (when they attend HLH to seek medical care) and analyzed at the laboratory facility in Haydom hospital. Results will be reported to the attending physician to assist patient treatment. Rapid malaria test (CareStart, USA) will be performed if relevant. CRP will be measured on all hospitalized children under one year with suspected infection to assist clinical evaluation of the infant. Blood cultures will be drawn from infants with fever or suspected infection. Blood culture bottles will be transported to the laboratory and will be incubated at 35°C in the BACTEC 9050® (Becton–Dickinson, Sparks, MD, USA) culture system for a maximum of 5 days unless flagged positive. Positive blood cultures will be sub-cultured on sheep-blood and chocolate agar using routine microbiological techniques. Furthermore, Gram stains will be made for all positive blood cultures. Antibiotic susceptibility testing (AST) will be performed on clinically relevant bacterial isolates using conventional methods (disk diffusion) following EUCAST guidelines (http://www.eucast.org/clinical_breakpoints/). All clinically relevant isolates (considered to cause infection) will be frozen at -80°C for subsequent genetic analysis (whole genome sequencing).

3.11.2 Laboratory tests which to be performed at UiB/SUH/UNN

Fecal samples and fecal swabs collected at six weeks and six months will be transported to Norway for the following analyses:

- Fecal swab samples (n=4000) collected at six weeks and six months will be screened for ESBL-E using a selective ESBL-screening agar (ChromID ESBL and ChromID Carba,

ProRIDE Trial in Tanzania

BioMerieux). All samples will be plated on non-selective plates for growth control.

ESBL-E isolates will be frozen for subsequent genetic analysis (whole genome sequencing and plasmid analysis).

- Fecal samples (n=4000) collected at six weeks and six months will be subjected to gut microbiota/metabolome and antibiotic resistome analysis using state of the art methods. . This will be done on DNA or metabolites extracted from the feces sampled and stored in a commercially available sampling kit (OMNIgen GUT/MET kits). In addition, fecal samples collected at six months will be analyzed to determine the levels of gut inflammatory markers between the two groups.

4.0 Monitoring of the study

Site monitoring will be conducted to ensure that the rights and well-being of study participants are protected. In addition, monitoring will verify that the reported clinical and laboratory data are accurate, complete and verifiable from source data. Site monitoring will also ensure that the conduct of the clinical trial is in compliance with the study protocol, good clinical practice (GCP) and good laboratory practice (GCLP) and applicable regulatory requirements. A data safety monitoring committee (DSMC) will be appointed and this DSMC will oversee that trial is conducted according to GCP and GCLP.

Table 2 showing monitoring plan

| | 1 st quarter | 2 nd quarter | 4 th quarter | 8 th quarter |
|-----------------|-------------------------|-------------------------|-------------------------|-------------------------|
| Enrolment visit | X | | | |
| Follow-up visit | | X | X | |
| Close up | | | | X |

Table 3 showing key activities of the clinical monitor

| Site visits | When | Key activities |
|-----------------------------------|-----------------------------------------------------|---------------------------------------------------------------------------------------------------------------------------------------------------------------------------------------------------------------------------------------------------------------------------|
| Monitoring visit during enrolment | One visit, four weeks since the start of enrolment. | Perform monitoring visit, to check for: - Inspection of all ICH GCP certificates in place - Verification of Informed consent forms - Eligibility check - eCRF completion - Equipment, consumables, study material - Review laboratory sample management |

ProRIDE Trial in Tanzania

| | | |
|------------------------------------|-------------------------------------------------------------|-----------------------------------------------------------------------------------------------------------------------------------------------------------------------------------------------------------------------------------|
| Monitoring visit follow up -first | One visit six months since the start of enrolment. | Perform monitoring visit, in particular check for: - Specimen collection procedure - Eligibility check - eCRF completion - Eligibility of source documents - Source data verification - Review AE/SAE reporting |
| Monitoring visit follow up -second | One visit 12 months since the start of enrolment. | Perform monitoring visit, in particular check for: - Specimen collection procedure - Eligibility check - eCRF completion - Eligibility of source documents - Source data verification - Review AE/SAE reporting |
| Close up visit monitoring | One visit 18 months since start of enrolment (end of study) | Perform monitoring visit, in particular check for: - Last query resolution - Storage and archiving of documentation - Review, update and finalization of IF |

5.0 Criteria for withdrawal of individual study participants

Study participants will be discontinued from participation in the study if:

- Any clinical adverse event (AE) during the four-week intervention, laboratory abnormality or other medical condition or situation occurs such that continued participation is not in the best interest of the participants
- Participants wishes voluntary withdrawal.
- Participants are free to withdraw from participating in the study at any time upon request.
- In any case participants will be given appropriate care under medical supervision until the symptoms of any AE resolve or the participant's condition becomes stable.

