2.3 Study end point measures

2.3.1 Primary end point

- Prevalence of the composite outcome death and /or hospitalizations at six months of age.

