19. Adherence and protocol deviations

Any deviations from the protocol will or have already been documented in a protocol deviation form and filed in the study master file. A SOP is in place describing the procedure for identifying non-compliances, escalation to the central team and assessment of whether a non-compliance /deviation may be a potential Serious Breach.

20. Analysis populations

The primary analysis will be an “intention to treat” analysis performed on all patients who were randomized. In addition, per protocol analysis will be performed for patients who reported to have adhered to the ingestion of the study product (probiotic or placebo), and on other subgroups of the study population.

Trial population

21. Screening data

Pregnant women in their last trimester, visited at home or attending the last antenatal care visit at HLH, will receive oral and written information about all aspects of the study before giving consent to let their future child participate in the study. Trained research assistants who speak the local language will be in charge of obtaining informed consent before recruitment.

22. Eligibility

Inclusion criteria

Healthy newborn infants with a birth weight (BW) equal or above 2.0 kg are eligible for inclusion. Newborn infants have to come from families who are long-term or permanent residents in the defined catchment area for this trial (30 km radius from HLH) in Tanzania. Parents have to be able and willing to complete study visit (including required study procedures) schedules over the six months proposed follow-up. This also includes that they, if possible, bring their child to the hospital in case of any intercurrent illness. Parents have to sign informed consent form (ICF) and have to agree that the child cannot participate in another clinical trial during the study period

Exclusion criteria

BW below 2.0 kg, refusal of informed consent and/or other health problems/illness including obvious congenital malformations

23. Recruitment

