Patients will be recruited among newborns; born at Haydom Lutheran Hospital (HLH) in North East Tanzania and out-born newborns in the surrounding area. HLH is located in the Mbulu district, at the western end of the Manyara region in the North-Central Tanzania, about 300 km south-west from regional center Arusha. The HLH catchment area consists of four administrative divisions, three districts and two regions. These are the Dongobesh and Haydom divisions in Mbulu District, the Basotu Division in Hanang District (Manyara Region), and the Nduguti Division in Iramba District (Singida Region). The hospital serves a population of more than two million people from five regions. Annually, there are more around 3900 deliveries in the hospital, and in 2018 the neonatal mortality rate in Tanzania was around 21/1000 live births.

24. Withdrawal / follow-up

Participation is based on informed voluntary consent of the parents of the child. Parents may decide that their child may withdraw at any time of the study without giving reasons or justification. Upon withdrawal, no further data will be collected. However, data recorded up until the time of withdrawal will be included in the analysis.

25. Baseline patient characteristics

Baseline data on demographic characteristics are recorded as detailed in the eCRF.

Analysis

26. Outcome definitions

Primary outcome

Prevalence (%) of the composite outcome death and/or hospitalizations at six months of age.

Secondary outcomes

- Rates (%) of ESBL-E colonization at six weeks and six months of age.
- Rates (%) of hospitalizations up to six months of age.
- Rates (%) of confirmed sepsis (blood culture-confirmed) episodes up to six months of age.
- Growth monitored by length and weight up to six months of age.
- Stool microbiota composition including resistome analysis (metagenome sequencing) at six weeks and six months of age.
- Stool metabolome composition at six weeks and six months of age.
- Stool inflammatory markers at six months of age
- Genetic characteristics of ESBL-E from colonization and clinical samples (targeted screening).
- Risk factors for death, hospitalization and sepsis.
- Primary and secondary outcomes will secondarily be performed stratified for place of delivery, ie hospital, home or primary health care facility.

27. Analysis methods

Clinical and microbiological data

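### Infants discontinued for an adverse event have no stated outcome follow-up to six months, so the intention-to-treat result may rest on untestable assumptions

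*Protocol*

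**What the plan says.** Protocol 5.0 sets out criteria for withdrawal and begins "Study participants will be discontinued from participation in the study if". The first ground is an adverse event during the intervention, a laboratory abnormality, or another medical condition or situation, limited by the clause "such that continued participation is not in the best interest of the participants". The only commitment after that point is clinical: "In any case participants will be given appropriate care under medical supervision until the symptoms of any AE resolve or the participant's condition becomes stable". Nothing is said about recording outcomes once an infant has been discontinued.

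SAP 24 covers withdrawal and follow-up, and is framed around parents: "Parents may decide that their child may withdraw at any time of the study". It continues "Upon withdrawal, no further data will be collected", with the qualification that "data recorded up until the time of withdrawal will be included in the analysis".

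The primary endpoint in Protocol 2.3.1 is "Prevalence of the composite outcome death and /or hospitalizations at six months of age". SAP 20 states: "The primary analysis will be an “intention to treat” analysis performed on all patients who were randomized". SAP 28 treats missing values as non-responses in the main analyses, and offers multiple imputation as a supplement that depends on how much is missing.

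**The concern.** The product is given for about four weeks, but the primary outcome runs to six months. If leaving the product for a medical reason also means leaving follow-up, outcome data go missing because of the infant's health, and possibly because of the assigned arm. Randomisation does not protect against that kind of loss.

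Three things are at stake:

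- **The composite.** The first death or admission is missed in infants discontinued before either has happened.
- **Mortality and the secondary endpoints.** Mortality is a separate objective (Protocol 2.2.1), and hospitalisation and confirmed sepsis are secondary endpoints (Protocol 2.3.2, SAP 26). An earlier admission does not make up for a later death, admission or sepsis episode that goes unrecorded.
- **The interim safety comparison.** Protocol 6.7 and SAP 13 compare mortality by arm at six weeks. Discontinuations in weeks 0 to 4 fall inside that window, so a death between discontinuation and week six could be missing from it.

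**Working it through.** **1. Do the two rules meet?** Protocol 5.0 places adverse-event discontinuation under a heading about withdrawal. SAP 24 is the only text on data after withdrawal and makes no exception. Neither document describes stopping the product for a medical reason while staying in outcome follow-up. The join is therefore the natural reading, but an inference.

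**2. How much follow-up is exposed?** Table 1 of the protocol puts the last visit at 25 to 27 weeks, taken here as 26. Discontinuation at week 4 leaves 26 − 4 = 22 weeks, about five months. At week 2 it leaves 24 weeks, about five and a half.

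**3. Which infants are affected?** Admissions are recorded (Protocol 3.8.2), one admission already meets the composite, and data before withdrawal are kept. For the composite, the loss is confined to infants discontinued without a prior admission.

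**4. The plan's own sample size.** Inputs from Protocol 3.4 and SAP 11 and 17: 9.0% v 5.4%, 85% power, two-sided 5%, 1:1 allocation.

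n = [1.960 √(2 × 0.072 × 0.928) + 1.036 √(0.09 × 0.91 + 0.054 × 0.946)]² / 0.036² = 924.2

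This reproduces the stated 924. Enrolling 1000 per arm allows for 76 losses (7.6%). That protects precision, not against loss related to outcome. Power with all 1000 per arm evaluable is 87.6%.

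**5. Illustrative odds ratios.** The documents give neither a withdrawal rate nor a later event risk, so both are assumed. With 1000 per arm, lost events = 1000 × share withdrawn × later risk. Withdrawn infants either stay in the denominator as event-free or are excluded. For example, with no true effect, 3% v 1% withdrawn and 30% later risk, 9 and 3 events are lost:

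- counted event-free: (81/919) / (87/913) = 0.925
- excluded: (81/889) / (87/903) = 0.946

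| True rates, probiotic v placebo (true OR) | Withdrawn | Later risk | OR, event-free | OR, excluded |
|---|---|---|---|---|
| 9.0% v 9.0% (1.00) | 3% v 1% | 30% both | 0.93 | 0.95 |
| 9.0% v 9.0% (1.00) | 3% v 1% | 50% both | 0.87 | 0.89 |
| 5.4% v 9.0% (0.577) | 3% v 1% | 30% both | 0.49 | 0.50 |
| 5.4% v 9.0% (0.577) | 1% v 3% | 30% both | 0.61 | 0.60 |
| 5.4% v 9.0% (0.577) | 2% v 2% | 30% both | 0.55 | 0.55 |
| 5.4% v 9.0% (0.577) | 2% v 2% | 18% v 30% | 0.58 | 0.58 |

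In the last row the 40% reduction also applies after withdrawal. Both arms lose the same share of events (3.6/54 = 6/90 = 6.7%), and there is essentially no bias. The cost is then power: 85.8% if 5% of events are lost in each arm, 83.8% if 10% are.

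**6. False-positive risk.** Take 9% in both arms, 1000 per arm, and events unrecorded in the probiotic arm only, with those infants counted as event-free. With observed difference d, the rejection probability is Φ[(d − 1.96 SE₀)/SE₁] + Φ[(−d − 1.96 SE₀)/SE₁], where SE₀ is the pooled and SE₁ the unpooled standard error. It is 6.8% with 5 events lost, 12.6% with 10 and 37.8% with 20, against the nominal 5%.

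**The case against.** Several stronger readings are tempting, and the documents do not support them.

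- **That data collection is stated to end at adverse-event discontinuation.** SAP 24 speaks of parents and does not name this route. The objection stands as to wording. It does not supply the missing follow-up rule.
- **That the sickest infants are lost.** An infant admitted before discontinuation is already counted in the composite. The best-interest clause also means that not every adverse event leads to discontinuation. A later first-event risk of 30% to 50% among infants not yet admitted is therefore purely an assumption, set against a planned 9% overall.
- **That the intention-to-treat analysis cannot be carried out.** All randomised infants can be analysed with partial data, under the missing-data rule in SAP 28 and its supplementary imputation. But the main rule does not say whether a missing outcome counts as event-free, as an event or as excluded. Imputation is conditional, and standard imputation assumes that the observed data explain the missingness, which is doubtful here.
- **That the bias favours the product.** If the product prevents illness, more placebo infants might be discontinued, and the estimate moves towards the null, as the fourth row of the table shows.
- **That harm is hidden.** SAP 13 and 15 have adverse events reported to the DSMB throughout. That limits the worry, but the plan does not say that this reporting continues for an infant already discontinued.

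A further objection is that SAP 20 contrasts a per-protocol analysis of adherent infants with intention to treat, so non-adherent infants evidently stay in. That is right for missed doses, but it does not cover an infant formally taken out of the study.

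**Conclusion.** The gap is real but narrower than it may first appear. Protocol 5.0 makes medical events a ground for leaving the study and provides no outcome follow-up afterwards, and the only rule on later data is that none are collected. Following the plan as read here leaves six-month status missing for health-related reasons in infants discontinued before a first admission. It also leaves later deaths, admissions and sepsis episodes missing for the mortality objective, the secondary endpoints and possibly the six-week DSMB comparison. The intention-to-treat result would then depend on assumptions that the trial's data cannot test.

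Neither the size nor the direction of bias can be determined from the documents. The illustrations run from essentially none, through 0.93 to 0.95 instead of 1.00, to 0.61 instead of 0.577 in the other direction. All depend on assumed withdrawal rates and later risks. The sample size is not at fault.

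**What to change.** - **Protocol 5.0:** leave the clinical criteria unchanged. Add that an infant discontinued for any reason other than withdrawal of consent to data collection still has death and hospitalisation recorded to six months, through the existing visits and hospital records.
- **SAP 24:** limit the rule against further data to parents' withdrawal of that consent. Report withdrawals by reason and arm.
- **SAP 28:** state how a missing primary outcome is coded in the main analysis, and add a sensitivity analysis for outcomes missing not at random, with assumptions allowed to differ by arm.
- **Infants already discontinued:** recover six-month vital status and admissions where consent allows, after checking the consent form.

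The required sample size does not change, and the visits and the hospitalisation CRF already exist. The cost is a small amount of extra follow-up and analysis. Timing limits the gain: SAP 11 puts the end of recruitment in January 2023 and the end of follow-up in July 2023, so the four-week intervention was over or nearly over for everyone when the SAP was written. Recovery will be partial for infants discontinued earlier, which makes the coding rule and the sensitivity analysis the more important part.
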